1. SYNOPSIS

Study Title	A pilot study evaluating the effectiveness of information and therapy guides for improving the psychosocial wellbeing of people with facial palsy.	
Study Design	Feasibility/pilot study	
Study Participants	Adults with a diagnosis of facial palsy and/or their friends and relatives	
Planned Sample Size	140 participants	
Planned Study Period	July 2019 – May 2021	
	Objectives	Outcome Measures
Primary	To evaluate the effectiveness of Information and Therapy guides (ITG) at improving the psychosocial wellbeing of people with a diagnosis of facial palsy	Hospital Anxiety and Depression Scale Face-Q – Social function Face-Q – Psychological function Face-Q – Appearance-related psychosocial distress Facial Disability Index
Secondary	To evaluate the effectiveness of Information and Therapy guides at improving the psychosocial welling of family and friends of people with a diagnosis of facial palsy	Hospital Anxiety and Depression Scale Adult Carer Quality of Life Questionnaire
Tertiary	To evaluate the acceptability and usability of Information and Therapy guides for people with facial palsy and/or their family and friends	Patient satisfaction questionnaire

2. ABBREVIATIONS

ANCOVA	Analysis of Covariance
CBT	Cognitive Behavioural Therapy
CI	Chief Investigator
CRF	Case Report Form
CTRG	Clinical Trials & Research Governance, University of Oxford
GCP	Good Clinical Practice
GP	General Practitioner
HRA	Health Research Authority
ICF	Informed Consent Form

ITG	Information & Therapy Guide
NHS	National Health Service
NRES	National Research Ethics Service
OXTREC	Oxford Tropical Research Ethics Committee
PI	Principal Investigator
PIL	Participant/ Patient Information Leaflet
R&D	NHS Trust R&D Department
REC	Research Ethics Committee
SOP	Standard Operating Procedure

3. BACKGROUND AND RATIONALE

Facial palsy is characterised by facial muscle weakness, typically due to facial nerve damage, and affects between 23 to 35 people per 100 000 (1). By far the most common cause of facial palsy is Bell's palsy, which affects approximately 20.2 people per 100 000 and is likely to have a herpetic trigger. Although up to 70% of people with Bell's palsy will make a full recovery, facial palsy is a condition with a heterogeneous presentation, with some people experiencing temporary unilateral weakness, with others having permanent, bilateral facial paralysis (2).

Some of the physical sequelae of facial palsy include difficulties with: eating, drinking, speaking, eyelid closure, pain, taste, muscle atrophy and synkinesis (3). Current management options include: injections of Botulinum Toxin A; facial therapy; facial reanimation surgery and surgery to the eyelid and/or tear duct (4). However, it is also important to note that it is not known how many patients with facial palsy have made a spontaneous recovery without treatment, as they are unlikely to present to facial palsy services.

Although there is no direct relationship between the degree of appearance change and reported distress (5), people with facial palsy typically experience higher levels of distress, compared to other forms of visible facial difference (6). This is believed to be due to the impact that facial palsy has on the face's ability to express emotions, which is a crucial aspect of face-to-face communication (7). This lack of facial expression of emotion can be interpreted by others as an indicator of boredom, hostility or disinterest, resulting in a higher number of negative social interactions (6). Indeed, impairment in smiling has been shown to be a significant predictor of anxiety and depression in individuals with facial palsy (8).

In a sample of 103 patients with facial palsy in the United Kingdom, 32.7% had significant levels of anxiety and 31.3% had significant levels of depression (5). This is compared to an estimated 8.33% for the general UK population (9). Furthermore, low self-esteem has been shown to be one of the strongest predictors of distress among people with facial palsy (10), indicating that difficulties with anxiety, depression and self-esteem are all significant factors which can affect the wellbeing of individuals with facial palsy.

Facial palsy can not only have an impact on the individual with facial palsy, but also on the physical and psychological wellbeing of friends, family members and carers. Indeed, the impact of caregiving on physical and psychosocial outcomes is well documented (11) and highlights the importance of focusing on not only the wellbeing of patients with facial palsy, but also their family members or carers.

The difficulties that patients across the United Kingdom experience accessing facial palsy services is well documented, with a freedom of information request in 2012 revealing that only 13% of Clinical Commissioning Groups routinely fund all types of facial palsy treatments, without requiring specialist funding approval (12). This means that patients often travel a long distance in order to access specialist multidisciplinary services, such as the Oxford Facial Palsy Service and may go some time without accessing support during the early stages of their condition.

Despite the significant impact of facial palsy on the psychosocial wellbeing of people with facial palsy, there is no research investigating the effectiveness of psychological interventions for people with this condition. As a result, a recent consensus document following a Delphi survey of patients, carers, clinicians and researchers highlighted research into identifying the types of psychological intervention that are most effective for people with facial palsy as being one of the key research priorities (13).

Although not researched yet in a facial palsy population, one type of psychological intervention that has been found to be effective at improving the psychosocial wellbeing of people with visible differences has been psychological self-help, including online or booklet-based self-guided cognitive behavioural therapy (CBT; see 14 for a review). With this in mind, the Oxford Facial Palsy Service secured funding from the charity “VTCT Foundation” to develop seven self-guided information and therapy guides (ITGs), for people with facial palsy and/or their friends or relatives, using evidence-based interventions such as cognitive behavioural therapy, social skills training and acceptance and commitment therapy.

This current study aims to pilot the use of these guides in order to assess their effectiveness at improving the psychosocial wellbeing of people with facial palsy and their friends and family. Eligible participants will complete a set of baseline measures prior to trialling the use of a relevant ITG over a period of four-to-six weeks. After the four-to-six weeks, participants will re-complete the measures completed at baseline, along with a questionnaire assessing the usability and acceptability of the ITGs.

4. OBJECTIVES AND OUTCOME MEASURES

Objectives	Outcome Measures	Timepoint(s) of evaluation of this outcome measure (if applicable)
Primary Objective To evaluate the effectiveness of Information and Therapy guides at improving the psychosocial wellbeing of people with a diagnosis of facial palsy	Hospital Anxiety and Depression Scale Face-Q – Social function Face-Q – Psychological function Face-Q – Appearance-related psychosocial distress	1) Prior to participant using ITG 2) After participant has used ITG for 4-6

	Facial Disability Index	weeks
Secondary Objectives To evaluate the effectiveness of Information and Therapy guides at improving the psychosocial welling of friends and relatives of people with a diagnosis of facial palsy	Hospital Anxiety and Depression Scale Adult Carer Quality of Life Questionnaire	1) Prior to participant using ITG 2) After participant has used ITG for 4-6 weeks
Tertiary Objectives To evaluate the acceptability and usability of Information and Therapy guides for people with facial palsy and/or their friends and relatives	Participant satisfaction questionnaire	1) After participant has used ITG for 2-3 weeks 2) After participant has used ITG for 4-6 weeks

5. STUDY DESIGN

Given that this study represents an initial pilot of the use of ITGs for people with facial palsy (and/or their friends and relatives), all eligible participants will receive the intervention (i.e. there will be no control group). As a result, this study will have a repeated-measures design.

Eligible participants will be recruited by one of two means:

- 1) Face-to-face of recruitment of OUH NHS patients during clinics at the Oxford Facial Palsy Service
- 2) Recruitment of people with facial palsy, not under the care of the Oxford Facial Palsy Service, through relevant web and social media pages (e.g. the Facial Palsy UK Facebook page)

Potential participants who have expressed an interest in the study will be provided with an information sheet and if still interested they will be invited to provide written consent (via an online consent form; Survey Hero). They will then be screened for eligibility using an online screening questionnaire (also Survey Hero). Participants recruited in Oxford Facial Palsy Service clinics will complete the screening questionnaire on the researcher's laptop during clinic or online at a later date if they wish to have more time to consider their participation in the study. Participants recruited on social media will be emailed a link to the screening questionnaire. Participants will have provided written consent for their email address to be shared with the research team.

Eligible participants will then be invited to complete baseline questionnaires:

People with facial palsy: Hospital Anxiety and Depression Scale; FACE-Q Satisfaction with appearance; FACE-Q Psychological function; FACE-Q Social function and Facial Disability Index.

Friends, relatives or partners: Hospital Anxiety and Depression Scale and Adult Carer Quality of Life Questionnaire.

Like the consent forms and screening questionnaires, baseline questionnaires will be completed online via Survey Hero.

Eligible participants will then be administered the relevant ITG. For eligible carers/relatives this will be the ITG entitled “Facial palsy: Advice for friends, family and partners”. For eligible participants with facial palsy, this will be determined by their score on the screening questionnaire. This process is outlined further in Section 7.2 ‘Screening and Eligibility Assessment’. Participants will then utilise the ITG over a period of four-to-six weeks. Half-way through the intervention period (after 2-3 weeks), they will receive an email reminding them to complete the ITG and will be provided a web-link to complete a questionnaire designed for the purpose of the current study measuring the participants’ ratings of acceptability and usability of the ITGs (participant satisfaction questionnaire) on Survey Hero.

At the end of the four-to-six week period, participants will be re-administered the baseline questionnaires (via web-link to Survey Hero), along with a questionnaire designed for the purpose of the current study measuring the participants’ ratings of acceptability and usability of the ITGs (participant satisfaction questionnaire). Participants will have a 2 week window to complete the final questionnaires after they have been sent to them at the end of the ITG trial period. If they do not complete the questionnaires in this window, they will be withdrawn from the study. Participants with facial palsy will also be re-administered the initial screening questionnaire. This will indicate whether the participant is eligible to complete a further ITG. If this is the case, then their post-intervention questionnaires will serve as a new baseline and the participant will be invited to complete the new ITG over a second four-to-six week period (followed by the same follow-up assessments as followed the first ITG). This process will occur up to a maximum of six times (reflecting the potential for a participant to trial all six ITGs). If they do not wish to complete further ITGs then the participant will be thanked for their involvement in the study and their involvement will be registered as ‘complete’. All participants will be provided with a separate email link to complete the relevant questionnaires at each stage (e.g. screening, baseline, 2-3 week satisfaction, 4-6 week final questionnaires). The email will also remind them of their unique ID number, for them to enter at the start of the questionnaires. This will help their responses to be matched with their previous responses.

We aim to trial the ITGs over a period of one year (July 2019 – May 2020). This will lead to the predicted sample sizes of 140 participants (120 with facial palsy, 20 per each of the 6 guides; 20 friends and family). This target is based on there being approximately 3000 people who have access to the Facial Palsy UK website. Given that approximately 1/3 people with facial palsy experience a significant level of distress (5); we hope that our ITGs would be relevant to, and accessible by, around 1000 people. 140 is therefore a conservative estimate of the number of participants that we will be able to recruit. Recruitment and completion will be monitored in case recruitment should be extended.

Participants recruited from OUH NHS Foundation trust will be provided with an information sheet during their clinic appointment with the Oxford Facial Palsy Service. Potential participants will then be given the option to either provide written consent in clinic using Survey Hero on the researcher’s laptop, or at a later stage (via weblink to Survey Hero consent form).

Participants recruited from social media will be provided with an information sheet via email and will provide written consent online using Survey Hero. Both people with facial palsy and their family members, friends and partners have access to Facial Palsy UK social media. Therefore both groups of participants can be recruited through this means.

6. PARTICIPANT IDENTIFICATION

6.1. Study Participants

Participants with a diagnosis of facial palsy, of any severity and aetiology or friends/relatives/partners of a person with facial palsy. In all instances participants will be aged 18 years or older.

6.2. Inclusion Criteria

Participant with Facial Palsy:

- Participant is willing and able to give informed consent for participation in the study.
- Aged 18 years or above.
- Current diagnosis of facial palsy, of any severity or aetiology.
- Participants experience one or more psychosocial difficulties related to facial palsy 'all the time' or 'a lot of the time', as assessed by a screening questionnaire (outlined in further detail in Section 7.2)

Participant who is a friend, family member or partner of someone with facial palsy:

- Participant is willing and able to give informed consent for participation in the study.
- Aged 18 years or above.
- Is a friend, family member or partner of an adult with facial palsy, of any severity or aetiology.
- Participants experience psychosocial difficulties related to supporting someone with facial palsy, as assessed by participant responding 'all the time' or 'a lot of the time' to one or more questions on a screening questionnaire (outlined in further detail in Section 7.2)

6.3. Exclusion Criteria

The participant may not enter the study if ANY of the following apply:

Participant with Facial Palsy:

- The participant is not in within the target age range (e.g. under the age of 18 years).
- They are not an individual with a current diagnosis of facial palsy.
- They do not speak enough English to understand the questionnaires or ITGs.

- They do not meet eligibility on the screening questionnaire (i.e. they 'never' or 'only occasionally' experience psychosocial difficulties associated with facial palsy (see section 7.2 Screening and Eligibility Assessment).

Participant who is a friend, family member or partner of someone with facial palsy:

- The participant is not in within the target age range (e.g. under the age of 18 years).
- They are not a friend, family member or partner of an adult with a current diagnosis of facial palsy.
- They do not speak enough English to understand the questionnaires or ITG.
- They do not meet eligibility on the screening questionnaire (i.e. they 'never' or 'only occasionally' experience psychosocial difficulties associated with supporting someone with facial palsy (see section 7.2 Screening and Eligibility Assessment).

Because participants will be using a unique ID number, it will not be possible for them to complete the screening questionnaire again, if their initial results indicate that they are ineligible. This is in order to prevent people from attempting screening multiple times to attempt to meet eligibility criteria.

Participants with facial palsy will not be matched with participants who are friends, family or a partner. Therefore, participants with facial will be eligible to participate, even if a friend, family member or partner does not participate. Likewise, a friend, family member or partner will be eligible to participate even if the person with facial palsy does not participate.

7. STUDY PROCEDURES

7.1. Recruitment

The participants in this study will be individuals with facial palsy and/or their family members/carers. They will be recruited by two means:

- 1) **Recruitment at Oxford Facial Palsy Service clinic appointments.** A member of the research team, who will also be a member of the care team, will approach eligible patients and/or friends or relatives during their clinic appointment. Given that all patients with facial palsy are eligible to take part in the study, it will not be necessary to review medical records prior to clinic to identify eligible participants. All potential participants will be provided with an information sheet, and opportunity to ask questions about the information sheet, at their clinic appointment.

Interested participants will provide written consent via completion of an online Consent Form (via Survey Hero). This will either be done in clinic on the researcher's laptop, or if patients would like more time consider their involvement this can be done remotely online via Survey Hero.

They will be given a signed copy of their completed consent form. Participants who have consented will then complete an online screening questionnaire (again either in clinic or remotely). If eligible, participants will complete baseline questionnaires via Survey Hero. Upon completion of questionnaires they will be sent the relevant ITG.

For potential participants who are the friend, family member or partner of someone under the care of the Oxford Facial Palsy service, the process will be the same as above, with participants who are a friend, family member or partner providing informed consent prior to completion of screening questionnaires.

- 2) **Online recruitment, including social media.** The United Kingdom's leading facial palsy charity, Facial Palsy UK, has agreed to support recruitment for the current study through their platforms, including their Facebook page and research emailing lists. Advertisements will include the contact details for the lead researcher and interested participants will be invited to email the lead researcher for further information about the research project, including the information sheet. Once the participant has read the information sheet and indicated that they are keen to take part in the study they will be emailed a link on Survey Hero to complete an online consent form. They will be provided an electronic copy of their completed consent form. If they consent to take part they will then be sent a link to an online screening questionnaire. If eligible, they will then be sent a link to complete baseline questionnaires. Upon completion of questionnaires, they will be sent the relevant ITG. They will be sent either a physical copy in the post or an electronic copy via email (as indicated during completion of the relevant section of the Survey Hero baseline questionnaires).

Advertisements will only directly target people with facial palsy themselves, rather than friends and relatives, with people with facial palsy being invited to take part and/or to nominate a friend or relative to take part.

Researchers will only be recruiting participants from within the United Kingdom.

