- 6) Facial palsy affects how I feel about myself (self-esteem) (**ITG = Facial palsy: building your self-esteem**)

Participants are invited to rate each statement according to how frequently they experience each difficulty. There are 5 options: all the time; a lot of the time; only occasionally; never or N/A. Participants are eligible to complete ITGs if they have rated having difficulties relating to the topic of the ITG 'all the time' or 'a lot of the time'. Participants will also be asked to rank the six statements in order of how much of a concern they are for them (1 = most important concern, 6 = least important concern). If participants are eligible to complete multiple ITGs (i.e. they rate experiencing difficulties 'all the time' or 'a lot of the time' for multiple topics), then they will complete ITGs in order of how much of a concern that area is for the participant. . They will be informed that they may be able to complete the next ITG that they are eligible for, at the completion of the 4-6 week trial period for their initial ITG.

At the completion of the 4-6 week trial period, participants will be invited to re-complete the original screening questionnaire and, if eligible (e.g. they still experience difficulties on one of the remaining topics 'all the time' or 'a lot of the time'), will be invited to trial the next ITG. If they do not wish to complete further ITGs then the participant will be thanked for their involvement in the study and their involvement will be registered as 'complete'

Participants who do not meet eligibility criteria will be thanked for their interest in the study and signposted to the Facial Palsy UK website for general information and advice for how to best manage facial palsy:

Thank you for your interest in this study. Unfortunately you do not currently meet the inclusion criteria for this study. For further information and advice about managing facial palsy please visit facialpalsy.org.uk or contact your NHS facial palsy service.

The screening questionnaires will also ask potential participants to provide information about their (or their family member or relative's) facial palsy diagnosis/type and date of onset.

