9.3. Analysis of Outcome Measures

A pre-post design will be used to determine whether the use of ITGs lead to a significant improvement in the psychosocial wellbeing of people with facial palsy and or their friends and relatives, as measured by the Hospital Anxiety and Depression Scale, Face-Q – Social function (people with facial palsy only), Face-Q – Psychological function (people with facial palsy only), Face-Q – Appearance-related psychosocial distress (people with facial palsy only) and the Facial Disability Index (people with facial palsy only). This change will be measured for each individual ITG, using paired-samples t-tests. The Facial Disability Index can also be used to control for improvement in facial palsy symptoms, when assessing the impact of ITGs on scores on measures of psychological wellbeing. In the instance of a significant change in facial palsy symptoms being observed, separate ANCOVAs will be used, with Facial Disability Index score being used as a covariate and scores on individual measures of psychosocial wellbeing serving as within-subjects factors.

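### Facial treatment during the 4-6 week window is neither an eligibility criterion nor described as recorded, and the conditional FDI adjustment only partly covers the gap, so some change may be wrongly attributed to a guide

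*Combined protocol and SAP*

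**What the plan says.** Section 7.1 (Recruitment) gives two routes. In the first, a member of the care team "will approach eligible patients and/or friends or relatives during their clinic appointment". Consent, screening and baseline can be completed on a laptop at that visit, or remotely later. The second route, in section 5, is "Recruitment of people with facial palsy, not under the care of the Oxford Facial Palsy Service, through relevant web and social media pages".

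Section 3 describes the usual care of the condition: "Current management options include: injections of Botulinum Toxin A; facial therapy; facial reanimation surgery and surgery to the eyelid and/or tear duct".

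Eligibility in section 6.2 requires "Current diagnosis of facial palsy, of any severity or aetiology". Nothing in 6.2 or 6.3 concerns recent, current or planned treatment. Section 7.2 says that screening also collects "information about their (or their family member or relative's) facial palsy diagnosis/type and date of onset". Sections 7.4 and 7.5 describe the baseline and follow-up forms as outcome scales plus a satisfaction questionnaire. On records, 7.1 says that "it will not be necessary to review medical records prior to clinic to identify eligible participants". No treatment log is described anywhere.

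Section 5 states that there is no control group. Sections 9.1 and 9.3 test each outcome for each guide with a paired t-test. Section 7.4 adds that the FDI lets the researchers control for change in facial symptoms, and 9.3 sets the condition: "In the instance of a significant change in facial palsy symptoms being observed, separate ANCOVAs will be used", with the FDI score as covariate.

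**The concern.** A person enrolled at a facial palsy appointment may receive facial treatment at or soon after the visit. Baseline can be taken that day. Follow-up questionnaires go out 4-6 weeks later and may be returned up to two weeks after that. Treatment in this interval is a rival explanation for any change in social function, mood or feelings about appearance, and a single-arm paired test cannot tell it from the effect of a guide. A participant may repeat the cycle for up to six guides, so one person can contribute several such windows.

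The primary objective is effectiveness, so a significant paired test will be read as evidence for that guide. As the data collection is described, a reader of the results could not see how many of a guide's users were treated in the window, or whether the change depends on them. The point concerns the six guides for people with facial palsy.

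**Working it through.** **1. The plan's own figure.** Section 9.2 gives 6 x 20 + 20 = 140, which reproduces. Each guide's paired test therefore rests on n = 20. No power analysis was done, so there is no power figure to reproduce. No significance level is stated; two-sided 5% is assumed, which is 2.5% in the direction of improvement.

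**2. Is treatment restricted or recorded?** Sections 6.2 and 6.3: no criterion. Section 7.2: diagnosis or type, and onset date. Sections 7.4 and 7.5: scales and satisfaction. Section 7.1: no record review to find eligible patients. None of these yields a treatment variable.

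**3. Size before any FDI adjustment.** Let q be the share of a guide's 20 users treated in the window, b the treatment effect in SD of change among untreated users, and the guide effect zero. Mean shift = q x b. Both q and b are assumptions.

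If the shift is spread equally over all users, the chance of declaring improvement comes from the non-central t with 19 degrees of freedom and non-centrality q x b x sqrt(20). In reality only some are treated, which widens the SD of change to about sqrt(1 + q(1-q)b²). For q = 0.25, b = 0.8 this is sqrt(1 + 0.12) = 1.06. For q = 0.5, b = 0.8 it is sqrt(1 + 0.16) = 1.08. The last column allows for this by simulation, with exactly 2, 5 or 10 of 20 treated.

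| Treated | b | Mean shift (SD) | Equal shift | Mixed treated and untreated |
|---|---|---|---|---|
| 2 of 20 (10%) | 0.4 | 0.04 | 4% | 4% |
| 2 of 20 (10%) | 0.8 | 0.08 | 5% | 5% |
| 5 of 20 (25%) | 0.4 | 0.10 | 6% | 6% |
| 5 of 20 (25%) | 0.8 | 0.20 | 13% | 11% |
| 10 of 20 (50%) | 0.4 | 0.20 | 13% | 13% |
| 10 of 20 (50%) | 0.8 | 0.40 | 40% | 34% |

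The nominal figure is 2.5%. The mixed column is the better estimate.

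**4. How far does the FDI rule help?** The ANCOVA runs only if the FDI change is itself significant. With n = 20, the power of that step is 14% for a mean FDI change of 0.2 SD, 25% for 0.3 and 56% for 0.5; 80% needs about 0.67.

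The full rule was simulated (40,000 trials per case, no guide effect), reading the ANCOVA as wellbeing change regressed on FDI change, with a test of the intercept. Treatment moves both measures by 1 SD, and the correlation between the two changes among people with the same treatment status is 0 or 0.4. These figures count significance in either direction, 5% nominal:

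- 25% treated: the ANCOVA is triggered in about 16% of trials. A guide effect is declared in 16% without adjustment, and in 14% (correlation 0) or 11% (correlation 0.4) under the plan.
- 50% treated: it is triggered in about 47%. The rate falls from about 47% to 33% or 23%.
- 10% treated: about 6-7% under the plan.

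The rule lowers the error but does not remove it.

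**5. What the FDI does not cover.** Section 7.4 describes it as physical and social function, so an effect on appearance need not register. Section 9.3 does not say which subscale is the covariate. The social subscale overlaps the wellbeing outcomes, and the FDI is itself listed as an outcome in section 4.

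**The case against.** The strongest reply is that the authors foresaw the problem. Sections 7.4 and 9.3 use the FDI for exactly this purpose, and where treatment moves facial function a good deal and wellbeing less, it works well. With 50% treated, an FDI effect of 1 SD, a wellbeing effect of 0.5 SD and correlation 0.4, the error rate falls from 18% to 7%. So although a reader might infer that change after physical treatment is simply credited to the guide, the documents do not support that. What stands is that the adjustment is conditional and incomplete.

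The treated share may also be low. The recruitment target in 9.2 is argued entirely from people with access to a charity website, and no clinic share is given. Section 3 reports that only 13% of commissioning groups routinely fund all treatment types without special approval, and section 8 notes limited surgery and botulinum toxin in the early stages. If treatment occurred only among clinic recruits and they were half of a guide's users, 50% treated would mean every one of them. Online recruits may be treated elsewhere, but the documents do not say how often. Baseline may also be completed after the visit, so treatment at the visit can precede it. This all bears on size and is why the 10% rows matter.

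Two further inferences go too far. One is that treated participants could never be identified afterwards: clinic recruits have medical notes (7.3) and an ID log links them to their data (10.2), although no extraction is described. The other is that some guide will be used mainly by clinic recruits: 7.2 allocates guides by screening answers and ranked concern, not by route.

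The appearance argument needs care too. Sections 1, 4 and 9.3 name an appearance-related distress scale, while sections 5 and 7.4 name a satisfaction-with-appearance scale. A distress scale may respond less directly to facial treatment.

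Finally, this is an openly uncontrolled pilot. That is a fair limit on what can be claimed, but it does not explain leaving an inexpensive, relevant variable uncollected when effectiveness is the primary objective.

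**Conclusion.** The point holds as a gap in data collection and analysis. Facial treatment in the window is neither a criterion nor described as recorded, one route enrols at a specialist appointment, and the FDI-adjusted ANCOVA is only a conditional, partial substitute. Some change may therefore be wrongly attributed to a guide.

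The size is unknown. At 10% treated the inflation is minor; at 50% with a 0.8 SD effect, before FDI adjustment, about a third of null guides would appear to work. The range rests on assumed treated shares, effects of 0.4-0.8 SD, an assumed direction (improvement within the window) and an assumed 5% level. The documents supply none of these, and as described the study would not collect the treated share either. The questionnaires themselves are not in the documents, so the absence of a treatment item is read from their descriptions. This is a worthwhile, cheap improvement and not a flaw that invalidates the pilot.

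**What to change.** - **Baseline form:** one self-report item on facial treatment, recent or planned, covering botulinum toxin, facial therapy and facial or eyelid surgery.
- **4-6 week form:** one item on facial treatment received since baseline, with date. Repeat it for each further guide.
- **Section 9.3:** pre-specify a sensitivity analysis of each pre-post change that omits guide-uses with facial treatment in the window, and report change descriptively by recruitment route (clinic or online).

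The cost is two short survey items and one extra table. Answers are self-reported, and subgroups within a guide of about 20 will be small, so the analysis is supportive only and will not settle attribution. It does make the treated share visible. No treatment is restricted or delayed.
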